### Data Synthesis

For dichotomous outcome measures Relative Risk (RR) will be calculated and significance testing completed using Chi-Squared or Fisher's exact test depending on sample sizes. For continuous variables standardised mean difference (SMD) will be calculated and unpaired, two-tailed student's t-tests used for significance testing.

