### Study Title

Peri-Operative Neutrophil:Lymphocyte Ratio (NLR) as a Predictor of Outcomes Following Emergency General Surgery During the COVID-19 Pandemic

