### Participants/Study Population

All adult patients (>17 years) undergoing emergency (general) surgery at a single centre (Queens Hospital, Romford, UK) regardless of COVID-19 status will be included. Patients will be organised into those with:

- a) suspected or confirmed COVID-19 (diagnosed clinically, radiologically or with positive viral PCR); and
- b) those for whom COVID-19 was not suspected.

Diagnosis or suspicion of COVID-19 must be made between 7-days before and 30-days after date of surgery in accordance with the COVIDSurg study criteria.

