### Planned Study Period

Data will be collected on all patients meeting criteria undergoing emergency surgery on or after the date of UK lockdown due to COVID-19 (23th March 2020) until 22nd May 2020. If sample size is small then the end date for data collection will be extended.

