### Study Questions

- 1) Is NLR a predictor of negative outcomes in patients undergoing emergency general surgery?
- 2) Is NLR different in COVID positive versus COVID negative patients undergoing emergency general surgery?

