### Primary Outcome

30-day mortality

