### Secondary Outcomes

7-day mortality  
Reoperation  
Length of stay  
Post-operative respiratory failure  
Post-operative ARDS  
Post-operative sepsis  
ITU/HDU admission

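### Question 1 on 30-day mortality: the stated relative-risk test needs an NLR grouping that the plan never defines, and no day from D0 to D3 is named as the predictor

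*Combined protocol and SAP*

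**What the plan says.** Study Questions asks, as Question 1, "Is NLR a predictor of negative outcomes in patients undergoing emergency general surgery". The Primary Outcome is "30-day mortality", which is dichotomous. The secondary outcomes are mostly dichotomous too, such as "ITU/HDU admission", but include the continuous outcome "Length of stay".

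Data Synthesis is two sentences. The first covers yes/no outcomes: "For dichotomous outcome measures Relative Risk (RR) will be calculated and significance testing completed using Chi-Squared or Fisher's exact test depending on sample sizes". The second gives continuous variables a standardised mean difference with an unpaired two-tailed t-test.

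The only groups in the plan are in Participants/Study Population, where "Patients will be organised into those with" suspected or confirmed COVID-19 and those without suspicion of it. Data Collection lists NLR at D0 (pre-operative), D1, D2 and D3. The title says only "Peri-Operative Neutrophil:Lymphocyte Ratio (NLR) as a Predictor of Outcomes". No section gives an NLR cut-off, a primary day, or a summary across days. Planned Study Period sets no target number: "If sample size is small then the end date for data collection will be extended".

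**The concern.** Both listed methods compare two groups. The COVID-19 groups serve Question 2; a relative risk of death between them says nothing about NLR. To answer Question 1 with the stated mortality test, someone must divide patients into high and low NLR, and the plan does not say where or on which day's value.

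The first question on the primary outcome can therefore be answered in many ways, and the choice can be made with outcomes in view. This is a practical possibility: the anticipated start is 25 May 2020 and eligible surgery begins on 23 March 2020, so anyone operated on by 25 April (25 April + 30 days = 25 May) would already have complete 30-day follow-up. At stake are the false-positive rate, if a day or cut-off is picked from the data, and power, if NLR is split.

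For length of stay, outcome and predictor are both continuous. Neither listed method relates them unless one is split.

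**Working it through.** **Inputs.** From the documents: a dichotomous primary outcome, four NLR values, relative risk with chi-squared or Fisher, and a two-tailed t-test. The plan states no sample size, event rate, effect size or alpha, so there is no figure to reproduce. Assumed for illustration: alpha 0.05; n = 150 or 300; mortality 5% or 10%; odds ratio 2 per SD of log NLR; log SD 0.8 for raw NLR. Mortality power is from 4,000 simulated datasets per setting.

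**1. Power for 30-day mortality (%).**

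| n, mortality | Median split, Fisher if any expected count <5 | Median split, chi-squared throughout | Firth logistic, log NLR | t-test, log NLR | t-test, raw NLR |
|---|---|---|---|---|---|
| 150, 5% | 19.5 | 28.5 | 43.5 | 44.1 | 45.5 |
| 150, 10% | 47.6 | 48.0 | 67.9 | 68.2 | 65.4 |
| 300, 5% | 48.3 | 48.9 | 71.0 | 71.3 | 67.8 |
| 300, 10% | 77.7 | 77.7 | 93.2 | 93.2 | 87.9 |

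Loss from splitting (Firth minus first column): 43.5 − 19.5 = 24.0; 67.9 − 47.6 = 20.3; 71.0 − 48.3 = 22.7; 93.2 − 77.7 = 15.5 points. With chi-squared throughout, the first loss falls to 43.5 − 28.5 = 15.0, so Fisher's conservatism explains 9 points of that cell. The other losses barely move. A repeat simulation gave 19, 48, 47 and 78% for the split and 42, 68, 68 and 93% for Firth.

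Hand check of the last row:
- *Split.* The odds ratio of 2 implies a relative risk of about 2.71 across the median. Risks are 0.20/3.71 = 5.39% and 20% − 5.39% = 14.61%, with 150 patients per half. Power ≈ Φ[(0.0922 − 1.96 × √(0.1 × 0.9 × 2/150)) / √(0.1461 × 0.8539/150 + 0.0539 × 0.9461/150)] = Φ[(0.0922 − 0.0679)/0.0342] = Φ(0.71) = 76%.
- *t-test.* The mean difference is about ln 2 = 0.693 SD. Power ≈ Φ[0.693 × √(30 × 270/300) − 1.96] = Φ(1.64) = 95%.

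Both agree with the simulation to within about 2 points.

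**2. Four days tested, none named.** If the days were independent, the chance of at least one false positive would be 1 − 0.95⁴ = 18.5%. With correlated days and four unadjusted t-tests, it is 16–17%, 12–14% and 9–10% at between-day correlation 0.5, 0.7 and 0.9. One named day gives 4.8–5.6%.

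**3. Cut-off searched for in the data, one day.** Taking the smallest p-value over 17 cuts (10th to 90th percentile) gives type I error of 18–27%; over nine deciles, 13–22%. Nine deciles with Pearson chi-squared throughout (n 100–400, mortality 5–15%) give 23–27%. The result depends on the number of cuts and the test, so roughly 13–27% is as precise as it can be.

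**4. Length of stay.** Assumed lognormal, log SD 1, log-scale correlation 0.2 with NLR. Power at n = 150 and 300: Spearman 66% and 91%; t-test of stay across a median NLR split 37% and 59%; t-test of NLR across a median stay split 41% and 66%. Splitting explains part of the shortfall: on the log scale it shrinks the correlation to 0.2 × √(2/π) = 0.160, and Φ(0.160√n − 1.96) is about 50% and 79%. The rest comes from applying a t-test to skewed values.

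**The case against.** The strongest reply is that the plan permits a test that works. NLR is continuous, deaths and survivors form two groups, and the second sentence of Data Synthesis allows a t-test between them. This needs no cut-off, and on log NLR its power matches the Firth model in every setting. That stands. A reader might infer from the table that the plan as written loses 16 to 24 points of power; the documents do not support this, because the loss arises only if NLR is split, and these figures only if it is split at the median. It would be equally wrong to call the t-test well powered: under these assumptions it passes 80% in one setting of four.

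A reader might also infer that it is an error not to give risk per unit of NLR. Question 1 asks only whether NLR is a predictor, so this output is a benefit of the model proposed below. Nor is lack of adjustment a mark against the t-test, since that model has NLR as its only predictor.

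Finally, the title and the four days may mean that a multi-day assessment is intended. If so, a stated summary or a multiplicity adjustment would close that gap as well as a single named day.

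What remains is that the plan assigns 30-day mortality to the relative risk, never says the t-test will be used for Question 1, and leaves the day open under either reading.

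**Conclusion.** The point holds in this form: for Question 1 the plan fixes neither the NLR grouping its stated mortality test needs, nor the day, nor which of two permitted tests will be used; and no listed method relates NLR to length of stay without splitting one of them. If NLR is split at the median, the cost is about 16 to 24 points of power. Four unadjusted days give a 9 to 17% chance of a false positive at between-day correlation 0.9 to 0.5, and a searched cut-off gives roughly 13 to 27%. All these sizes rest on assumed inputs; the gaps in the text do not. Nothing in the documents shows that a day or cut-off has been picked from the data, or that Question 1 cannot be answered. This is a cheap improvement that replaces an open choice with a better, stated method.

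**What to change.** In Data Synthesis, for Question 1:

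- Analyse 30-day mortality and the other binary outcomes by logistic regression on continuous log2(NLR), Firth-penalised if events are few. Report the odds ratio per doubling and the AUC, each with a 95% CI.
- Name in advance one primary NLR time point (for example the pre-operative sample), or one multi-day summary, or a multiplicity adjustment across days. With a single primary time point, treat the other days as secondary. For any value after D0, count only events after that sample.
- For length of stay, report the Spearman correlation with a 95% CI.
- Keep the relative risk and the SMD with t-test for comparisons by COVID-19 status (Question 2). Report any high/low NLR relative risk as descriptive, at a cut-off fixed before outcomes are examined.

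The cost is a reworded section, a little more analysis, and sampling and event dates added to the extraction template, which is to be piloted and refined anyway. No extra patients are needed. Intervals will be wide if deaths are few. At a true AUC of 0.69 (Φ(0.693/√2)), the Hanley–McNeil 95% CI is about 0.47–0.91 with 7 deaths in 150 patients, 0.54–0.84 with 15 in 300 and 0.58–0.80 with 30 in 300, so at the low end the AUC may be uninformative.

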### Data Collection

Data will be collected using a data extraction template. This will be piloted on 5 included patients and refined as appropriate. Data will be collected from electronic sources including (but not limited to) BlueSpier, EPRO, Cyberlab and Medway. Data will include baseline patient characteristics, operation performed, COVID status and diagnostic method, NLR (pre-operative/day 0 (D0), D1, D2 and D3) and the aforementioned outcome measures. Data will be collected for 30-days following on from the date of surgery.

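### Length of stay falls to a t-test and SMD with no rule for in-hospital deaths or patients still admitted at day 30, so a mortality difference can distort the stay comparison

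*Combined protocol and SAP*

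**What the plan says.** The outcome appears in the Secondary Outcomes list only as "Length of stay", with no start point, end point or scoring rule. The Data Synthesis section has one rule for dichotomous outcomes and one for everything continuous: "For continuous variables standardised mean difference (SMD) will be calculated and unpaired, two-tailed student's t-tests used for significance testing". The Data Collection section sets the horizon: "Data will be collected for 30-days following on from the date of surgery".

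Death is central to the study. The primary outcome is "30-day mortality", and "7-day mortality" is among the secondary outcomes. The first study question is "Is NLR a predictor of negative outcomes in patients undergoing emergency general surgery". No NLR cut-off is given, so the plan does not define two NLR groups whose stays could be compared.

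**The concern.** A hospital stay can end in discharge or in death, and here it can also be cut short when data collection stops at day 30. Raw stay mixes the three: a death on day 3 scores the same as a discharge home on day 3. If NLR does predict death, as the study sets out to test, then any higher-NLR and lower-NLR groups will differ in how often stay is ended by death. A t-test on raw stay cannot separate slower recovery from earlier death.

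Leaving deaths out instead conditions the comparison on survival. The plan chooses neither rule, so the choice could be made after the data are seen. At stake is whether the reported stay difference describes recovery, mortality or a blend of the two.

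**Working it through.** The plan gives no sample size, event rate, standard deviation or alpha, so it has no figure to reproduce. The check asks how far the planned comparison moves under stated assumptions.

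**Assumed inputs (none from the documents).** Recovery time is log-normal with median 7 days and log-SD 0.8. A fraction p of each group is assigned a potential death time, exponential with mean m of 2 to 14 days. Stay is the earliest of recovery, death and day 30. The two groups stand for any higher- and lower-mortality groups that a t-test might compare.

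**Formula.** Let S(t) be the probability that recovery takes longer than t.

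- Mean stay without death: A = ∫₀³⁰ S(t) dt
- Mean stay of those assigned a death time: B(m) = ∫₀³⁰ S(t)·exp(−t/m) dt
- Group mean: (1 − p)·A + p·B(m)

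**Values of the integrals (days).**

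| Median recovery | A | B(2) | B(14) |
|---|---|---|---|
| 7.0 | 9.188 | 1.815 | 5.959 |
| 7.7 (10% longer) | 9.989 | 1.841 | 6.314 |
| 8.4 (20% longer) | 10.761 | 1.862 | 6.643 |

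**Step 1: equal recovery, 16% vs 4%.** The difference is −(0.16 − 0.04)·(A − B).
- m = 2: −0.12 × (9.188 − 1.815) = −0.88 days
- m = 14: −0.12 × (9.188 − 5.959) = −0.39 days

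The true difference in recovery is zero. The SMD runs from about −0.125 to −0.055.

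**Step 2: 20% longer recovery in the higher-mortality group, 16% vs 4%.** Without deaths: 10.761 − 9.188 = +1.57.
- m = 2: (0.84 × 10.761 + 0.16 × 1.862) − (0.96 × 9.188 + 0.04 × 1.815) = 9.337 − 8.893 = +0.44
- m = 14: (0.84 × 10.761 + 0.16 × 6.643) − (0.96 × 9.188 + 0.04 × 5.959) = 10.102 − 9.059 = +1.04

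The loss is 1.13 to 0.53 days. Steps 1 and 2 together give the range of about 0.4 to 1.1 days.

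**Step 3: 10% longer recovery, 25% vs 5%.** Without deaths: +0.80. With deaths: −0.87 (m = 2) to +0.04 (m = 14). Here the sign can reverse.

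**Step 4: the day-30 cut alone.** Uncapped log-normal means are 7·e^0.32 = 9.64 and 8.4·e^0.32 = 11.57, a difference of 1.93. The cut lowers it to 1.57, a loss of about 0.35 days with no deaths at all.

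**Step 5: what the tests do.** Simulation with 100 per group, two-sided 0.05, mean death time 2 / 7 / 14 days:

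| Test | Equal recovery: rejects | 20% longer recovery: shows longer stay |
|---|---|---|
| t-test on raw stay | 15 / 10 / 7% | 6 / 12 / 18% (about 32% without deaths) |
| Cause-specific log-rank for discharge | 5.5 / 5.4 / 4.8% | 29 / 30 / 31% |
| Gray's test | 45 / 23 / 14% | 84 / 69 / 59% (includes mortality) |

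**Step 6: the scoring rule on its own.** This uses a different assumed model: 40 vs 110 patients, median stay 10 vs 7 days, 30% vs 5% mortality, log-normal death times with median 5 days.

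| Rule | Difference (days) | Power |
|---|---|---|
| Stay counted to death, capped at 30 | 1.47 | 0.21 |
| Deaths and day-30 inpatients dropped | 2.36 | 0.41 |
| Survivors only, capped at 30 | 3.25 | 0.52 |
| Deaths scored as 30 days | 7.49 | 0.99 |

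**Step 7: late deaths.** Suppose all assigned deaths occur in hospital, survivors' stay is equal and mortality is 16% vs 4%. The difference is then 0.12 × [m(1 − e^(−30/m)) − 9.188]: −0.86 at m = 2, +0.04 at m = 10 and +0.38 at m = 14.

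**The case against.** - **The plan never says that stay goes to a t-test.** NLR is itself continuous, and the second study question, NLR by COVID status, is a direct use for an SMD and t-test. With no NLR cut-off, the two groups modelled above are not groups that the plan defines. This stands: the application to stay is an inference, though the natural one, because no other listed outcome is continuous and no other method is offered.
- **A Fine-Gray analysis is not a cure.** It responds to mortality more than the t-test does. Under equal recovery Gray's test rejects in 45 / 23 / 14% against 15 / 10 / 7%. This stands, and it is why the cause-specific ratio should lead.
- **A one-sentence survivors-only rule would do nearly as well.** In the same scenarios a survivors-only t-test rejects in 4.5 / 5.7 / 5.3% under equal recovery and finds the longer stay in 28 / 23 / 25%. This stands only in part. It conditions on survival, and it weakens when sicker patients die: in the Step 6 model, a latent correlation of 0.4 between long stay and death cuts its difference from 3.25 to 1.93 days. It suits a labelled sensitivity analysis.
- **Every input is assumed, and direction depends on when deaths occur.** True, and Step 7 shows a zero or opposite effect. This limits any claim about size and sign. It does not touch the omission.

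A reader might also add the COVID timing rule, "Diagnosis or suspicion of COVID-19 must be made between 7-days before and 30-days after date of surgery", since longer stays give more time to be diagnosed. That is a group-classification problem that arises with no deaths at all. It is separate and lends no weight here.

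**Conclusion.** The concern holds in limited form. The omission is certain: no section says how in-hospital deaths or day-30 inpatients count towards length of stay. That the t-test applies to stay is the natural reading of Data Synthesis rather than its stated text.

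On the assumed inputs, a mortality difference of 16% vs 4% shifts the stay comparison by about 0.4 to 1.1 days, and detection of a 20% longer recovery falls from about 32% to 6–18% with 100 per group. The percentages are assigned (potential) deaths. Under equal recovery, realised in-hospital deaths are 14.5% vs 3.6% at mean death time 2 days and 6.8% vs 1.7% at 14 days. The day-30 cut separately lowers the 20% difference from about 1.9 to 1.6 days.

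A reader might infer that the stay result will be reversed, or that the mortality findings are compromised. Neither follows. Reversal needs a large mortality difference with early deaths, the documents give no rates from which to predict it, and the primary outcome does not use length of stay. This is a modest weakness in one secondary outcome that should be corrected.

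**What to change.** In Data Synthesis, replace the t-test and SMD for length of stay with wording such as:

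> Length of stay will be analysed as time from surgery to discharge alive, censored at day 30, with in-hospital death as a competing event. The main measure will be the cause-specific hazard ratio for discharge alive, with pre-operative (D0) NLR as a continuous variable. The cumulative incidence of discharge alive (Fine-Gray) will be reported beside it as a combined measure of stay and mortality, not of stay alone. Raw stay will be described as median and IQR, separately for survivors and deaths. A survivors-only comparison may be added as a labelled sensitivity analysis.

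Entering D0 NLR as a continuous variable also removes the need for a cut-off. If modelling proves infeasible, the minimum is to define the start and end of stay, state how deaths and day-30 inpatients count, and report median and IQR by survival status without the t-test.

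**Cost.** A few sentences, a little more analysis work and less familiar effect measures. Discharge and death dates must be on the extraction template, which Data Collection already allows to be refined after the 5-patient pilot. The cause-specific ratio is not immune to bias: under equal recovery it stays at 1.00 when death is unrelated to recovery time, but drifts to 1.02–1.14 if long-stay patients are also likelier to die (assumed latent correlation 0.3 to 0.6). The Fine-Gray ratio moves to 0.75–0.88 under equal recovery through deaths alone, so it must be labelled as above.

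### The Question 2 comparison of NLR by COVID group is crude only and cannot separate COVID from surgical case mix; an adjusted estimate should be reported beside it

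*Combined protocol and SAP*

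**What the plan says.** Study Questions, item 2, reads "Is NLR different in COVID positive versus COVID negative patients undergoing emergency general surgery". Participants/Study Population takes "All adult patients (>17 years) undergoing emergency (general) surgery at a single centre" and divides them into patients with suspected or confirmed COVID-19 and "those for whom COVID-19 was not suspected". It does not restrict by diagnosis or operation and has no matching rule.

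Data Collection states: "Data will include baseline patient characteristics, operation performed, COVID status and diagnostic method, NLR". NLR is recorded pre-operatively (D0) and on D1, D2 and D3.

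Data Synthesis is the whole analysis plan. Binary outcomes get a relative risk with a chi-squared or Fisher's exact test. For the rest, "For continuous variables standardised mean difference (SMD) will be calculated and unpaired, two-tailed student's t-tests used for significance testing". No section describes regression, stratification, a comparison of case mix between the COVID groups, or a sensitivity analysis. The operation and the baseline characteristics are collected but given no role in Question 2.

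**The concern.** The cohort is open to every kind of emergency general surgery, so the two COVID groups may differ in the operations performed and in age. If those factors are related to NLR, the difference in group means is the COVID difference plus whatever the difference in case mix contributes. The two parts cannot be told apart from an SMD and a p-value. The added part can run either way: it can produce a difference where COVID has none, or hide one that exists.

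What is at stake is how one of the two study questions can be interpreted. The primary outcome, 30-day mortality, is not touched by this point.

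**Working it through.** **Is there a figure to reproduce?** No. The document gives no sample size, power, effect size, SD, group ratio or case-mix share. Planned Study Period says only "If sample size is small then the end date for data collection will be extended". Every number below is therefore an assumed input, used to show how the mechanism works and not to predict this study's bias.

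**Structure.** Let *p*(C) and *p*(N) be the shares of patients in the higher-NLR stratum in the COVID and non-COVID groups. Let *g* be the NLR gap between strata and *d* the true COVID difference within strata. Then

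crude difference = *d* + *g* × (*p*(C) − *p*(N)).

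The second term vanishes only if the strata do not differ in NLR or the groups have the same mix.

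**Illustration 1, ratio scale, no COVID effect.** Let *k* be the NLR multiple for major against minor operations. On the log scale *g* = ln *k*, so the spurious geometric-mean ratio is *k* raised to the difference in shares.

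| *k* | 60% vs 40% major | 70% vs 30% major |
|---|---|---|
| 1.5 | 1.5^0.2 = 1.08 | 1.5^0.4 = 1.18 |
| 2 | 2^0.2 = 1.15 | 2^0.4 = 1.32 |

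The ratio is above or below 1 according to which group has more major operations. These ratios belong to a log-NLR analysis. They cannot be converted to the planned SMD without a within-group SD, which the document does not give.

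**Illustration 2, SD scale, simulated.** Assumptions: normal outcome with within-stratum SD 1, two strata, shares symmetric about 50%, two-sided 5% test, 20,000 data sets per scenario. The SMD is the crude difference divided by √(mean of the two group variances), where each variance is 1 + *g*²*p*(1 − *p*). For example, with *g* = 1 and 65% vs 35%, SMD = 0.30 / √(1 + 0.2275) = 0.27.

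Rejection rates with no COVID effect:

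| Gap *g* | Imbalance (points) | Spurious SMD | t-test, 30 vs 90 | t-test, 50 vs 150 |
|---|---|---|---|---|
| 0.5 | 20 | 0.10 | 7.5% | 8.7% |
| 0.5 | 40 | 0.20 | 15.1% | 22.1% |
| 1.0 | 20 | 0.18 | 13.3% | 19.5% |
| 1.0 | 30 | 0.27 | 25.0% | 37.9% |
| 1.0 | 40 | 0.36 | 40.0% | 59.8% |

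At the mild end (gap 0.5, 10 points) the spurious SMD is only 0.05. With the stratum in a linear model, rejection is 4.7% to 5.2% in every tabulated scenario.

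Masking, with a gap of 1 and the imbalance running against the COVID effect:

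- True effect 0.3, 30 points: crude difference 0.3 − 1 × 0.3 = 0, and the t-test rejects about 5%. The adjusted estimate is 0.30, with rejection in 27% (30 vs 90) or 42% (50 vs 150).
- True effect 0.5, 50 vs 150: t-test rejection falls from 77% with balanced mix to 20% at 30 points and 9% at 40 points.

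The simulated adjustment works fully because the stratum is observed without error. Operation class would be an imperfect marker of surgical disease, so in practice adjustment would remove only part of such a bias.

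**The case against.** - **The question is descriptive.** Item 2 asks whether NLR differs, not whether COVID raises it, and a crude difference answers that. This stands. A reader might infer that the planned contrast is wrong, or that the plan makes a causal claim. The document supports neither inference, so the adjusted estimate should not replace the crude one.
- **The mechanism comes from outside.** No section says that operation type or age is related to NLR, or that the groups differ in either. A reader might go further and infer that any NLR difference found will be an artefact of surgical disease. That cannot be supported: size and direction are unknown, and the bias could be negligible.
- **The comparator is already restricted.** Both groups come from the same hospital, calendar window and emergency setting. This controls for those factors, and the fact that every comparator patient needed emergency surgery is equally true of the COVID group. Only a difference in mix matters. But nothing prevents one, and no planned table would reveal it.
- **Adjustment is imperfect.** D0 NLR precedes surgery, so operation class is there only a proxy for disease, and diagnosis is not listed among the data items. If COVID status influenced which operation was done, adjusting may remove part of the association. Both points stand and are reasons to show both estimates.
- **Another problem may matter more.** "Diagnosis or suspicion of COVID-19 must be made between 7-days before and 30-days after date of surgery", whereas NLR stops at D3. That is a separate issue, and case-mix adjustment would not resolve it.

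**Conclusion.** The concern holds in a limited form. The crude contrast is a legitimate descriptive answer to Question 2, but it cannot separate COVID from operation type and age, and the plan does not use the collected data that would help.

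Whether this matters depends on two conditions that the document does not settle: that these factors are related to NLR, and that they are unevenly spread between the groups. On the assumed inputs, the spurious geometric-mean ratio is 1.08 to 1.32. For imbalances of 20 to 40 points, the nominal 5% error becomes 7.5% to 40% with 30 vs 90 patients and 8.7% to 60% with 50 vs 150. These figures show what could happen; they do not estimate what will. The change is worth making because it is cheap and affects the reading of one of only two study questions.

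**What to change.** In Data Synthesis, for Question 2:

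1. Keep the crude difference at each time point as the descriptive answer.
2. Beside it, report the COVID-group coefficient, with its confidence interval, from a linear model of log NLR that includes age and operation class. The exponentiated coefficient is a geometric-mean ratio. Give the crude ratio on the same scale so that the two can be compared.
3. Define operation class before analysis (for example minor or major), derived from the operation already recorded. No section defines such classes at present.
4. Tabulate age and operation class by COVID group.
5. State that a difference will be attributed to COVID only if it persists after adjustment. Persistence is necessary for that reading but not sufficient, since disease severity is only partly captured.

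**Cost.** One model at each of four time points and one table. Operation is already collected. Age is not named as a data item, but it is an ordinary baseline characteristic and is needed to apply the age criterion for entry. With a two-level class and linear age, the model spends two degrees of freedom. Precision will suffer somewhat if the COVID group is small. The proxy problem at D0 and the possible over-adjustment remain, and the write-up should say so.
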